Prevention seeking behavior (at baseline)	Patient Characteristics	HealthVerity Vaccine Data	
These variables will be assessed during the 12 month baseline period:
 
Telephone or Telehealth visits defined as a claim with any of the following procedure codes (G2012, G2010, G2061-G2063; 99205-99205, 99212-99215, 99421-99423, 99441-99443, G0425-G0427, G0406-G0408)
 
COVID-19 laboratory tests defined as a claim with any of the following CPT-4 codes (87635, 86318, 86328, 86769, 87426, 86408, 86409, 86413)
 
Flu vaccinations defined as a claim with the following procedure codes (90653-90664, 90666-90668, 90724, 90470, 90672, 90673, 90685-90688)
 
The cumulative proportion of IC and non-IC subjects receiving their first dose of COVID-19 vaccine, by month, starting from December 2020 until most recent data.

Acute Respiratory Infection Hospitalization (at baseline)	Patient Characteristics	HealthVerity Vaccine Data	Any inpatient claim that occurs in the 12 month baseline period with a diagnosis of J00-J06, J09-J18, J20-J22 will be reported
Follow-up time	Patient Characteristics	HealthVerity Vaccine Data	The number of days between the index date and the earliest of the following: end of the study or end of continuous insurance enrollment
IS drugs use	Patient Characteristics	HealthVerity Vaccine Data	The proportion of subjects with IC conditions and usage of IS drugs for >14 days during the baseline period will be reported, as well as use within 14 days and 28 days within receipt of the first vaccine dose. IS drugs exclude low-dose [<60mg/day] prednisone.

PFIZER CONFIDENTIAL

Table 3. Patient Characteristics and Vaccine Utilization variable definitions

Variable	Role	Data source(s)	Operational definition
COVID-19 supportive medication use	Patient Characteristics	HealthVerity Vaccine Data	The use of medications considered supportive for COVID-19 will be assessed in the 12-month baseline period including remdesivir, dexamethasone, doxycycline, norepihephrine, methylprednisolone, lopinavir/ritonavir, eculizumab, sarilumab, tocilizumab, losartan, azithromycin, hydroxychloroquine, siltuximab, colchicine, and convalescent plasma. Codes used to identify these treatments will be based on the Sentinel COVID-19 Natural History Master Protocol

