Other baseline medication use	Patient Characteristics	HealthVerity Vaccine Data	Medications for pre-existing conditions per the Sentinel COVID-19 Natural History Master Protocol (eg, angiotensin converting enzyme inhibitors (ACE), angiotensin-receptor blockers (ARB)).
Vaccine utilization	Patient Characteristics	HealthVerity Vaccine Data	Patterns of uptake. The proportion of IC and non-IC patients who are partially and fully vaccinated with BNT162b2 (or any other vaccines), at different calendar months and follow-up periods (eg, 7 days post dose 2, 14 days post dose 2). Mean, median, minimum, and maximum time between receipt of the first and second dose of BNT162b2 (or any other vaccine)

Table 4. Breakthrough Cases Definition

Variable	Role	Data source(s)	Operational definition
Breakthrough SARS-CoV-2 infection	Outcome	HealthVerity Vaccine Data	Among patients who meet the definition of fully vaccinated, a breakthrough SARS-CoV-2 infection will be defined by evidence of a claim with a diagnosis code of U07.1 that occurs >14 days after the second vaccination date. The first claim with a diagnosis of COVID-19 after this time will be used to assess mean and median time from the second dose until the breakthrough case

PFIZER CONFIDENTIAL

Table 5. COVID-19 Healthcare resource use and Costs definitions

Variable	Role	Data source(s)	Operational definition
Emergency department (ED) visit	Outcome	HealthVerity Vaccine Data	An outpatient claim with a place of service = 23 that occurs after the breakthrough COVID-19 diagnosis date or at the same time/episode of care
Outpatient Hospital Visit	Outcome	HealthVerity Vaccine Data	An outpatient claim with a place of service = 22 or 19 or a standard billing code that begins with '13' that occurs after the breakthrough COVID-19 diagnosis date or at the same time/episode of care
Other Outpatient Visit (not ED, not hospital-based)	Outcome	HealthVerity Vaccine Data	An outpatient claim that does not meet the definition for an ED visit or Outpatient hospital visit.
Hospitalization	Outcome	HealthVerity Vaccine Data	A record from the chargemaster data with encounter type of Inpatient OR a series of claims (separated by no more than 2 days) with a place of service = 21 or standard billing codes that begin with '11' or '12' that occur after the breakthrough COVID-19 diagnosis or at the same time/episode of care 1 st admission and readmissions will be differentiated.

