8.7. Data analysis

Data analyses will follow extensive feasibility analyses aimed at determining whether a full study and the assessment of vaccine effectiveness are feasible, as illustrated below:

Study implementation approach

Characteristics of the IC, non-IC and total population (IC + non-IC) groups will be described. Descriptive statistics for continuous variables will include N (number of patients), mean, median, standard deviation, Q1, Q3, minimum, and maximum. Categorical variables will be described using frequency counts and percentages.

The incidence rate of breakthrough cases of SARS-CoV-2 infection will be determined based on the following:

- Among fully vaccinated patients, those who have a claim for COVID-19 (ICD-10-CM: U07.1) that occurs on or after >14 days following their second dose of an mRNA vaccine (or 1st dose of Johnson & Johnson) will be considered to have had a breakthrough event. The time from 14 days after the qualifying dose until the breakthrough event will be the person time at risk.

PFIZER CONFIDENTIAL

- Among fully vaccinated patients with no evidence of COVID-19 after their qualifying dose, the time from 14 days after the qualifying dose until the end of follow-up will be the person time at risk.

[figure not shown]
The incidence rate of breakthrough cases of SARS-CoV-2 infection will be calculated as the number of patients who experience the event divided by the observed time at risk, and reported per 100 person years. Poisson 95% confidence intervals will be reported for the incidence rates.

Absolute effect measures such as risk difference between non-IC and IC will be reported. Time period specific effect estimates (eg, at 6 months after vaccination) may be estimated if feasible. The characteristics of the breakthrough infections will be described, including clinical presentation and severity.

The primary analysis will describe results among the non-IC cohort and the IC cohort who are vaccinated with BNT162b2. Subgroup analyses will include results for clinically meaningful subgroups as defined by vaccination type, relevant patient characteristics (eg, age), and each IC condition as listed below:

- HIV/AIDS
- Solid malignancy
- Bone marrow transplant
- Organ transplant (excluding bone marrow)
- Rheumatologic/inflammatory
- Primary Immunodeficiencies
- Other immune condition
- CKD or ESRD
- Hematologic malignancy

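### Detection of mild breakthrough infection may differ between IC and non-IC subjects, and the plan commits to no severe-outcome rate or follow-up testing count that would show it

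*Combined protocol and SAP*

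**What the plan says.** - **Outcome.** In Table 4 (section 8.3), "a breakthrough SARS-CoV-2 infection will be defined by evidence of a claim with a diagnosis code of U07.1 that occurs >14 days after the second" dose. There is no test-result or symptom criterion.
- **Aim 2 measure.** Section 8.7: "The incidence rate of breakthrough cases of SARS-CoV-2 infection will be calculated as the number of patients who experience the event". The denominator is person-time, and the result is scaled to 100 person-years. For precision, "Poisson 95% confidence intervals will be reported for the incidence rates".
- **Contrast.** Section 8.7 also commits to a comparison of the cohorts: "Absolute effect measures such as risk difference between non-IC and IC will be reported".
- **Severity (Aim 3).** Section 8.7: "The characteristics of the breakthrough infections will be described, including clinical presentation and severity". Categorical variables are summarized as counts and percentages. Hospitalization, ICU use, ventilation and death in Table 5 are all tied to the breakthrough diagnosis. The hospitalization entry accepts any inpatient stay during or after that episode, with no COVID-19 cause and no time limit. No rate of severe disease per person-time is specified.
- **Who is IC.** Under section 8.2.1, IC status by diagnosis needs one inpatient stay or two separate outpatient dates in the baseline year. The remaining route is use of immunosuppressive drugs. Non-IC subjects need continuous enrollment and a vaccine record, but no other contact with care.
- **Testing.** Table 3 has "COVID-19 laboratory tests defined as a claim with any of the following CPT-4 codes", but only for the 12-month baseline. Section 8.4 confirms that the data source holds COVID-19 tests.
- **Handling.** In section 8.7, matching, regression and propensity scores are optional and exploratory, with age and time from vaccination as example confounders. The example sensitivity analyses concern enrollment and the IC definition. Section 8.9 admits misclassification and underreporting in general, without saying that they may differ by cohort.

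**The concern.** An infection that produces no claim counts as event-free time. Whether a mild infection produces a claim depends on whether the subject seeks care or is tested, and the two cohorts differ by construction in the contact with care required of them. A difference in the U07.1 rate between IC and non-IC can therefore reflect detection as well as risk. The Poisson interval covers sampling error only and gives no warning of this.

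The severity description inherits the problem, because its denominator is the detected cases. If IC subjects have more mild infections detected, the hospitalized percentage is diluted. If they are also admitted more often for other reasons, or are screened at admission, the percentage is raised. The planned outputs give no means of telling which effect dominates. What is at stake is the reading of the IC versus non-IC risk difference and of the severity percentages when the two cohorts are set side by side.

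**Working it through.** The plan states no expected rate, sample size or testing frequency, so there is no figure of its own to reproduce. The check is a simple detection model in which every input is an assumption.

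**Inputs.** L is the true infection rate per 100 person-years, h the true hospitalized fraction, and d the probability that a non-hospitalized infection receives a U07.1 claim. All hospitalized infections are taken as detected.

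**Formulas.**
- Observed rate = L × [h + (1 − h)d]
- Hospitalized share of detected cases = h / [h + (1 − h)d]
- Hospitalized rate = L × h, which does not involve d

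**Equal true risk.** Set L = 1 and h = 0.10 in both cohorts, that is, 0.9 mild and 0.1 hospitalized infections per 100 person-years. For example, with d = 0.60 the rate is 0.9 × 0.60 + 0.1 = 0.64 and the share is 0.1 / 0.64 = 15.6%.

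| d non-IC | d IC | Rate non-IC | Rate IC | Ratio | Share non-IC | Share IC |
|---|---|---|---|---|---|---|
| 0.30 | 0.30 | 0.37 | 0.37 | 1.00 | 27.0% | 27.0% |
| 0.40 | 0.50 | 0.46 | 0.55 | 1.20 | 21.7% | 18.2% |
| 0.30 | 0.45 | 0.37 | 0.505 | 1.36 | 27.0% | 19.8% |
| 0.30 | 0.60 | 0.37 | 0.64 | 1.73 | 27.0% | 15.6% |
| 0.45 | 0.30 | 0.505 | 0.37 | 0.73 | 19.8% | 27.0% |

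The hospitalized rate is 0.10 versus 0.10 in every row. The last row shows that the bias reverses if detection is lower in IC subjects. L cancels from the ratios and shares. The spurious rate difference scales with L: at L = 1 it is 0.55 − 0.46 = 0.09 or 0.64 − 0.37 = 0.27 per 100 person-years in the second and fourth rows.

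**Range.** For h from 0.05 to 0.20, with d = 0.30 in non-IC and 0.40 to 0.60 in IC, the spurious rate ratio runs from 1.18 to 1.85. The ratio of hospitalized shares (IC to non-IC) runs from 0.85 to 0.54.

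**Masking.** Suppose IC infections are truly 1.5 times as likely to be hospitalized (h = 0.15 versus 0.10).
- Equal detection at 0.30: IC share 0.15 / 0.405 = 37.0%, share ratio 1.37.
- IC detection 0.45: 0.15 / 0.5325 = 28.2%, share ratio 1.04.
- IC detection 0.60: 0.15 / 0.66 = 22.7%, share ratio 0.84.

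**Any-cause admissions.** Now let a fraction q of detected mild IC cases count as hospitalized for another reason, and none in non-IC, with h = 0.10 and d = 0.45 versus 0.30.
- IC share = (0.10 + 0.405q) / 0.505.
- This equals the non-IC share of 27.0% when q = (0.2703 × 0.505 − 0.10) / 0.405 = 0.09.
- Below about 9% IC disease looks milder than it is; above that it looks more severe. At q = 20% the share ratio is 1.33.
- The hospitalized rate is affected as well. At q = 10% it is 0.10 + 0.0405 = 0.1405 in IC against 0.10, a ratio of about 1.4.

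A hospitalized rate built on the present Table 5 definition would therefore not solve the problem. It needs a COVID-19-specific definition.

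**The case against.** A reader might infer that IC subjects are tested more, so that their infection rate will be inflated and their disease will look milder. The documents do not support that. They give no testing rates for either cohort, and baseline contact makes unequal detection plausible without establishing it. Non-IC subjects are also vaccinated enrollees with a year of medical coverage. The milder appearance is not assured either, because any-cause admissions can cancel or reverse it.

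Other points against the concern have weight:
- Aims 2 and 3 are worded for IC subjects, not as comparisons, and section 8.5 calls the study mainly descriptive. Describing severity among cases answers Aim 3 as written, and no formal IC versus non-IC severity contrast is stated. However, section 8.7 does commit to a risk difference and describes results in both cohorts.
- Severity is not reported only as a percentage. Counts are planned too, and with cohort person-time a crude rate could be derived. It would still use the any-cause definition, and no such rate or interval is committed.
- Baseline tests, telehealth visits and influenza vaccination are tabulated, and the lists of confounders and sensitivity analyses are open-ended. This allows an analysis of unequal detection but does not commit to one. Baseline testing does not show testing while at risk.
- A hospitalized rate is not free of bias. Incidental positives can restore a spurious IC excess, and the equal hospitalized rates in the table hold because the model assumes complete detection and no such admissions.

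**Conclusion.** The concern holds in conditional form. The outcome depends on detection, the cohorts differ by design in required contact with care, a between-cohort difference will be reported, and nothing committed in the plan would reveal or limit unequal detection. If detection of mild infection is higher in IC subjects, the infection rate and risk difference are biased upward. Under equal true risk and a 10% true hospitalized fraction, the spurious rate ratio is 1.20 at 50% versus 40% detection and 1.73 at 60% versus 30%. If detection is lower in IC subjects, the bias runs the other way.

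The hospitalized share among cases is unreliable for comparing cohorts, but the direction of its error cannot be stated from the documents. All sizes rest on assumed detection probabilities and hospitalized fractions, and on full detection of hospitalized infections. The planned outputs remain computable and valid as descriptions of diagnosed infection. It is their IC versus non-IC interpretation that is unprotected, so this is a change the sponsor should make, not a flaw that stops the study.

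**What to change.** 1. In section 8.7, keep the any-U07.1 rate. Beside it, add the incidence of hospitalized breakthrough infection per 100 person-years of the fully vaccinated cohort, for IC, non-IC and each IC group, with the same Poisson interval.
2. In Table 5, add a definition for that outcome, such as U07.1 coded on the inpatient record, in principal position where available to limit incidental positives.
3. Report this rate next to the case-based counts and percentages, and rest any IC versus non-IC severity comparison on it.
4. Apply the Table 3 COVID-19 test codes to the at-risk period and report tests per person-year by cohort.
5. In section 8.9, state that under-ascertainment may differ between IC and non-IC subjects.

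The cost is one new outcome definition and two additional tables from data already held. Hospitalized events will be fewer and intervals wider, notably in the smaller IC groups, and some incidental admissions will remain.

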7. RESEARCH QUESTION AND OBJECTIVES

The overall objective of this study is to evaluate characteristics, vaccine utilization and outcomes among vaccinated subjects with IC conditions. The primary analysis will be conducted on subjects vaccinated with BNT162b2. A variety of subgroup analyses are planned, along with multiple sensitivity analyses that will test how variations in study design affect results.

Primary Objectives:

Aim 1: Describe profiles, vaccine utilization and resource use among subjects with IC conditions vaccinated with BNT162b2

Aim 2: Evaluate incidence rates of breakthrough infections among subjects with IC conditions fully vaccinated with BNT162b2

Aim 3: Evaluate the clinical presentation of vaccine breakthrough cases among subjects with IC conditions, including time to infection and severity of disease (hospitalization, mortality)

Secondary Objectives

Evaluate Aims 1, 2, 3 and HCRU/costs over time and stratified by relevant patient characteristics (eg, age), in specific IC conditions and by vaccination type (eg, any Mrna).

Exploratory Objective

Generate early estimates of the effectiveness of BNT162b2 in preventing COVID-19 infection, stratified by relevant patient characteristics (eg, age), in specific IC conditions.

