- IS drug use: >14 days IS medications (chemotherapy, immuno-modulators (IM), or corticosteroids excluding low-dose [<60mg/day] prednisone – See Drug List) and not falling into any of the above 9 condition groups
- >14 days of anti-metabolite use and not falling into any of the above 10 condition or drug use groups
- More than 1 IC condition

PFIZER CONFIDENTIAL

Analyses for younger cohorts (eg, 12-15) will also be conducted, as data accumulates.

For the exploratory aim, the Screening Method will be used to calculate VE for the overall study population of subjects with an IC condition and also stratified VE estimates for the different immunocompromised subject groups, with VE also determined for those subjects with >1 IC condition²⁶. We will use the proportion of the population that are vaccinated (PV) and the proportion of subjects with breakthrough SARS-CoV-2 infections that are vaccinated (PCV) to calculate VE using the following formula:

$$VE = (PV - PCV) / [PV(1-PCV)]$$

where PV = the proportion of the population that is vaccinated (ie, vaccination coverage) and PCV = the proportion of subjects with breakthrough SARS-CoV-2 infections that are vaccinated.

Additionally, breakthrough incidence rates and VE will be stratified by age at diagnosis (eg, < 65 and \geq 65 years of age at index vaccination).

Sensitivity analyses will be conducted to test the robustness of findings by varying key study design aspects (eg, continuous enrolment, IC case definition) and data analysis techniques. Other statistical techniques (eg, matched analyses, multiple regression, propensity scores) may be applied on an exploratory basis after careful examination of potential confounders (eg, age, time from vaccination). Exploratory analyses related to alternate dosing may also be conducted upon feasibility results, and as recommendations from public health authorities evolve. The analyses (entirely or in part) will be conducted over time and updated on a rolling basis as monthly data cuts become available.

While the analyses will be focused on the IC population, analyses will also be conducted (in part or entirely) on the non-IC population, the total (IC + non-IC) population or relevant subgroups (eg, other high-risk conditions, vaccination status) to support the interpretation of findings.

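### The exploratory VE is committed only as a crude screening-method figure per IC group, without a confidence interval, so age mix alone can shift VE between IC conditions

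*Combined protocol and SAP*

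**What the plan says.** The exploratory objective in section 7 is to "Generate early estimates of the effectiveness of BNT162b2 in preventing COVID-19 infection, stratified by relevant patient characteristics (eg, age), in specific IC conditions".

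Section 8.7 gives the method: "the Screening Method will be used to calculate VE for the overall study population of subjects with an IC condition". The printed formula takes one PV and one PCV and has no covariate term. The same calculation is then to be repeated by condition, since the plan promises "also stratified VE estimates for the different immunocompromised subject groups, with VE also determined for those subjects with >1 IC condition".

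On age, section 8.7 says "breakthrough incidence rates and VE will be stratified by age at diagnosis (eg, < 65 and" the complementary band from 65 upward. The two bands are introduced as an example. Nothing says how stratum values are combined, or whether the per-condition VE is the split or the un-split figure.

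On adjustment: "Other statistical techniques (eg, matched analyses, multiple regression, propensity scores) may be applied on an exploratory basis after careful examination of potential confounders". Age is one of the confounders named there.

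On precision: "Poisson 95% confidence intervals will be reported for the incidence rates". No interval is specified for VE. Section 8.5 plans no sample size calculation, and section 8.9 (limitations) does not mention confounding of VE.

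**The concern.** Section 6 says that further study is needed to learn which IC conditions carry reduced VE. The VE values will therefore be read across conditions, and the 12 mutually exclusive groups are likely to differ in age. A pooled PV and a pooled PCV do not give a weighted average of the age-specific VEs. If older people are both more often vaccinated and at a different risk of infection, pooling shifts the result, and the shift depends on each group's age mix. Two conditions with the same true VE can then show different values. Without an interval, the reader also cannot tell a small group's noise from a real difference.

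**Working it through.** The plan states no PV, PCV, case count or VE, so there is no figure to reproduce. The printed formula is algebraically sound: it equals 1 − [PCV/(1−PCV)] × [(1−PV)/PV]. For example, PV 0.60 and PCV 0.25 give 0.778 both ways.

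**Set-up (all values assumed).** Two age bands; coverage c = 0.45 (<65) and 0.80 (≥65); true VE identical in both. Let w be a band's share of the group and r its relative infection risk if unvaccinated.
- Unvaccinated cases: U = Σ w·r·(1−c)
- Vaccinated cases: V = Σ w·r·c·(1−VE)
- PV = Σ w·c
- Crude VE = 1 − (V/U) × (1−PV)/PV

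**Example.** True VE 0.60, risk 1:2 (young:old), half the group aged ≥65:
- U = 0.5×1×0.55 + 0.5×2×0.20 = 0.475
- V = (0.5×1×0.45 + 0.5×2×0.80) × 0.40 = 0.410
- PV = 0.625
- Crude VE = 1 − (0.410/0.475) × (0.375/0.625) = 0.482

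**Changing only the age mix, at true VE 0.60:**

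| Share aged ≥65 | Risk 2:1 (young:old) | Risk 1:2 | Risk 1:1 |
|---|---|---|---|
| 0% | 0.600 | 0.600 | 0.600 |
| 20% | 0.647 | 0.517 | 0.600 |
| 50% | 0.686 | 0.482 | 0.600 |
| 90% | 0.657 | 0.560 | 0.600 |

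Two groups must be compared within one column, because the risk gradient belongs to the epidemic. A group with 20% aged ≥65 and one with 90% differ by 1 point (2:1) or 4 points (1:2). The largest gap over all mixes is about 9 points (2:1) or 12 points (1:2), and it needs one group lying wholly in one band. Crude 1−VE is true 1−VE times a factor that does not depend on VE. At true VE 0.80 every gap is therefore halved, since 0.20/0.40 = 0.5; for example, risk 1:2 with 50% aged ≥65 gives 0.741.

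**What a split at 65 leaves.** In the set-up above the split removes all the bias by construction. If coverage still varies below 65, some remains. Assume 30% and 60% coverage in two equal halves of the under-65s, risk 2:1 and true VE 0.60:
- U = 0.5×2×0.70 + 0.5×1×0.40 = 0.90
- V = (0.5×2×0.30 + 0.5×1×0.60) × 0.40 = 0.24
- PV = 0.45
- Crude VE = 1 − (0.24/0.90) × (0.55/0.45) = 0.674

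With 20% or 80% of the under-65s in the higher-coverage part, the same formula gives 0.644 or 0.659. The bias stays at 4 to 7 points, but the gap between groups shrinks to 1 to 3 points.

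**Effect of the fix.** Within a band, the odds of vaccination among cases divided by c/(1−c) equal 1−VE. Under 65: (0.45×0.40/0.55)/(0.45/0.55) = 0.40. From 65: (0.80×0.40/0.20)/(0.80/0.20) = 0.40. A model with offset logit(PV) by band therefore returns VE 0.60 whatever the age mix.

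**Precision.** Eight vaccinated among 20 cases at PV 0.60 give VE = (0.60−0.40)/(0.60×0.60) = 0.56. The exact binomial interval on 8/20 is 0.191 to 0.639, which maps to VE −0.18 to 0.84. At PV 0.50 and true VE 0.60, PCV = 0.4/1.4 = 0.286. The log-odds interval, 1 − 0.4 × exp(±1.96 × √(1/V + 1/U)) with V and U now case counts, is 0.12 to 0.82 with 30 cases, 0.38 to 0.74 with 100 and 0.51 to 0.67 with 500.

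**The case against.** Three arguments in the plan's favour have weight.

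- **The age split is not capped.** A reader might infer that VE will have at most two age bands. The documents do not say so: the split at 65 is an example, section 7 asks for stratification by patient characteristics within IC conditions, and Table 3 already defines finer age categories. This stands. The gap is that no combined, age-adjusted VE is committed to.
- **Adjustment is foreseen.** Section 8.7 commits to sensitivity analyses that vary the analysis technique, lists matching, regression and propensity scores, and names age as a confounder. This stands in part, but those techniques are optional and not tied to the VE estimate.
- **The bias may be small.** A reader might set 69% against 48% in the 50% row and take 20 points as the possible gap between two conditions. That contrast reverses the risk gradient and leaves the mix unchanged, so it does not describe two groups in the same data. With one gradient, groups are biased in the same direction and much of the bias cancels. With equal risk across ages there is none. Nor do the documents state a VE difference that the study is meant to detect.

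The aim is also exploratory, described as early estimates and subject to feasibility. That lowers the weight of the point. It does not supply the missing interval or a rule for combining strata.

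**Conclusion.** The point holds in a limited form. The per-condition VE that the plan commits to is unadjusted and has no stated interval, and age mix can create differences between conditions with equal true VE. Under the assumed coverage (45%/80%) and a 2:1 gradient in one direction, the between-group gap is about 1 to 12 points at true VE 60% and half that at 80%. The upper end needs very unequal age mixes. The bias requires both coverage and infection risk to vary with age, and the documents give neither. It lies mainly in the un-split group figures, since splitting at 65 removes part of it. The formula itself is not wrong; the weakness is applying it once to a group of mixed age. The missing interval is a gap whatever the size of the bias. The change should be made, in proportion to an exploratory aim. How PV and PCV are defined and dated is a separate matter.

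**What to change.** Amend section 8.7 so that the main VE estimate is a logistic model of vaccinated status among cases with offset logit(PV).

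- Take PV by the age categories of Table 3 within the population being estimated. Merge categories where PV is 0 or 1 or rests on few subjects, because logit(PV) is then undefined or noisy.
- Add region or payer (both defined in Table 3) only where cells allow. A full age by region by payer cross-classification within 12 groups would be too sparse.
- Report 1 − exp(coefficient) with a 95% CI overall and by IC group.
- Label any un-split formula VE as crude and give it a CI too.
- Fix age at a date that exists for unvaccinated cases. The present sentence refers both to age at diagnosis and to age at index vaccination.

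The cost is about a paragraph of text and modest programming, using variables already planned. Intervals will be wide in small IC groups, and the offset treats PV as known, so the CIs will be somewhat too narrow where PV comes from few subjects.
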